Sample size calculations for the primary endpoint (rate of cytology testing) are based on a pairwise comparison of observed changes from baseline in clinic-specific three-month testing rates between intervention study arms (APP or APP+PCA) and the control arm, using a t-test adjusted for clustering on the clinic level. The baseline rate in control clinics is assumed to be approximately 50%, consistent with the preliminary data presented above. Assuming that there will be no observed change in rates for control clinics during the testing period, our expected sample size of 9030 (i.e. 3010 per arm, seven clinics per arm, and an average of 430 women per clinic) will be sufficient to provide 90% power to detect a between-arm difference as small as 16% as significant. This calculation assumes a quite conservative value for the intracluster correlation of outcomes within clinics of 0.07, and is based on a 1% significance level to account for the fact that there will be two pairwise comparisons with the control arm (i.e. one per intervention arm). Accounting for as much as 10% missing data on testing rates, we will still retain more than 90% power to detect differences of this magnitude or larger between arms as significant at the 5% level. We should also retain adequate power to conduct additional sensitivity analyses investigating the possible confounding influence of clinic-level descriptors (e.g. race/ethnicity and age distribution) on observed results. Finally, we note that our proposed analysis that will account for within-clinic paired observation of outcome rates and adjust for baseline covariates will likely yield more power than the conservative estimates made above. Although the study is not powered to detect significant differences between intervention groups, a similar calculation for the comparison between the APP and APP+PCA groups indicates that we retain at least 70% power to detect a difference in observed changes in testing rates as small as 15% as significant at the 5% level.

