Parallel calculations for the secondary colposcopy outcome also are based on between-arm comparison of changes in three-month colposcopy rates from baseline levels, and assume that approximately 50% of women will receive cytology at baseline and follow-up in the control group, and that colposcopy rates will also remain unchanged at 13%. We also assume that the intervention-related reduction in cytology will result in approximately 20% fewer women eligible for colposcopy at follow-up. Based on similar assumptions about intracluster correlation and loss to follow-up, results indicate that with the planned total sample size of 9030, we will retain at least 80% power to detect an intervention-related reduction in colposcopy rate as small as 8% at the 5% (one-sided) significance level. Due to our conservative assumptions, we should have sufficient power to detect even smaller intervention-related effects in analyses adjusting for baseline characteristics.

We did not perform calculations for the testing interval length and LEEP outcomes because of the lack of preliminary data on their potential variability within and between clinics.

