**a) Decrease the rate of cervical cytology testing among women ages 21-29 years of age**

**Pre:** Rate of women 21-29 years of age who received cervical cytology tests over total number of women 21-29 years of age in quarter (3 months) before start of intervention

**Post:** Rate of women 21-29 years of age who received cervical cytology tests over total number of women 21-29 years of age in months 3-6, 9-12, and 15-18 after intervention started

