The primary outcome measure will compare the observed within-clinic changes in cervical cytology testing rates between intervention and comparison groups using a t-test accounting for clinic-level clustering. We will use the same approach to test differences between each of the APP and APP + PCA and the comparison groups. Tests will be adjusted for multiple comparisons. Secondary endpoints include examining the interval between tests for women who received two cervical cytology tests from the same provider and the decrease in the number (and percent) of women receiving colposcopy procedures and LEEP or cryotherapy procedures. These will be analyzed using a similar approach as adopted for the primary endpoint. Patient satisfaction surveys will be administered to all women evaluated and compared between interventions and the controls. Because most available data is on the clinic level, we will have limited opportunities to analyze patient-level data. However we will be able to conduct supplementary analyses to investigate the possible impacts of between-arm imbalances in clinic level characteristics such as racial/ethnic composition, age distribution, descriptors of lab procedures, additional app or educational materials that are not part of the assigned intervention, and cervical cancer screening educational activities. Prior to starting the intervention and during the study, administrators and physicians at each clinic site will be asked about possible confounding variables at their clinic.

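### The stated 90% power for the primary endpoint does not follow from the printed inputs, and the input that the planned change analysis needs is not given

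*Combined protocol and SAP*

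**What the plan says.** All power statements are in the section Sample Size Estimates and Power Calculations.

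- The primary calculation is "based on a pairwise comparison of observed changes from baseline in clinic-specific three-month testing rates", each intervention arm against control, using a t-test adjusted for clustering. It takes a 50% baseline rate, no change in control clinics, 7 clinics per arm, an average of 430 women per clinic and 3010 women per arm. It concludes that this "will be sufficient to provide 90% power to detect a between-arm difference as small as 16% as significant".
- On clustering and alpha: "This calculation assumes a quite conservative value for the intracluster correlation of outcomes within clinics of 0.07, and is based on a 1% significance level". Sidedness is not stated.
- With up to 10% missing data: "we will still retain more than 90% power to detect differences of this magnitude or larger between arms as significant at the 5% level".
- On pairing, the text says that to "account for within-clinic paired observation of outcome rates and adjust for baseline covariates will likely yield more power than the conservative estimates made above".
- For colposcopy, with similar but unnumbered clustering assumptions: "at least 80% power to detect an intervention-related reduction in colposcopy rate as small as 8% at the 5% (one-sided) significance level".

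Under Data Analyses, the primary analysis will "compare the observed within-clinic changes in cervical cytology testing rates between intervention and comparison groups using a t-test accounting for clinic-level clustering". The post-intervention rate is measured "in months 3-6, 9-12, and 15-18 after intervention started". How the three windows are combined is not stated.

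**The concern.** With 7 clinics per arm and an ICC of 0.07, the number of clinics limits precision far more than the number of women does. Ninety per cent power at a 1% level for a 16-point difference looks too high for that design. A change-from-baseline analysis could do better, but only if clinic rates are strongly correlated over time, and no such correlation is given. The paragraph also describes pairing as extra power on top of its figures, which suggests that the 90% does not depend on pairing.

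This paragraph is the plan's only justification for 7 clinics per arm on the primary endpoint. If the trial finds no difference, a reader who trusts the 90% could wrongly conclude that a 16-point effect has been excluded.

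**Working it through.** **Inputs (Sample Size Estimates and Power Calculations).** k = 7 clinics per arm, m = 430 women per clinic, ICC 0.07, control rate 0.50, alpha 1%, difference 16%, stated power 90%.

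**Assumptions.** The 16% is read as percentage points (50% vs 34%), which favours the plan. Clinics are taken as equal in size. Both sidedness options are shown. Each is computed with a normal reference (z) and with a noncentral t on 12 df (14 clinics less 2), or on 18 df if variance is pooled over three arms (21 less 3).

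**1. Attempt to reproduce the 90% (unpaired).**

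- Design effect = 1 + (430 − 1) × 0.07 = 31.03
- Effective n per arm = 3010 / 31.03 = 97.0
- SE = √[(0.50×0.50 + 0.34×0.66) / 97.0] = √(0.4744 / 97.0) = 0.0699
- 0.16 / 0.0699 = 2.29

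| Power at 1% | t, 12 df | t, 18 df | z |
|---|---|---|---|
| Two-sided | 28% | 31% | 39% |
| One-sided | 38% | 42% | 48% |

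The stated 90% is not reproduced. If 16% were relative (50% vs 42%), SE = 0.0713 and power is 5–7% two-sided or 9–11% one-sided.

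**2. Is the number of women the reason?** With unlimited women per clinic, SE = √(0.4744 × 0.07 / 7) = 0.0689. Two-sided power at 1% rises only to 29% (t, 12 df) or 40% (z).

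**3. Missing-data statement (5% level, 10% missing).** 387 women per clinic; design effect 1 + 386 × 0.07 = 28.02; effective n 2709 / 28.02 = 96.7; SE = 0.0700. Power is 56% (t, 12 df) to 63% (z) two-sided, or 69% to 74% one-sided. The plan says more than 90%.

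**4. What would give 90% at 16 points and 1%?**

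- *Unpaired:* an ICC of 0.016 (t, 12 df) to 0.023 (z) two-sided, against the stated 0.07.
- *Change analysis, SD of clinic-level change:* SD = SE / √(2/7). The SE needed at two-sided 1% is 0.0355 (t, 12 df), 0.0376 (t, 18 df) or 0.0415 (z). The SD may then be at most 6.65, 7.0 or 7.8 points. One-sided, the limits are 7.3 (t, 12 df) to 8.3 (z) points.
- *Change analysis, ICC 0.07 kept:* the variance of one observed clinic rate is v_c = 0.25 × 31.03 / 430 = 0.0180 at 50%, and v_t = 0.2244 × 31.03 / 430 = 0.0162 at 34%. Let r be the correlation between observed clinic rates in any two periods, and average J post windows (equal correlation between all periods is an assumption):

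Var = [2v_c + (v_c + v_t)(1 + (J − 1)r)/J − 2r·v_c − 2r·√(v_c·v_t)] / 7

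| Two-sided 1%, t on 12 df | r = 0.5 | r = 0.7 | r = 0.8 |
|---|---|---|---|
| One window (J = 1): SE | 0.0709 | 0.0549 | 0.0449 |
| One window: power | 27% | 48% | 69% |
| Three windows (J = 3): SE | 0.0583 | 0.0452 | 0.0369 |
| Three windows: power | 42% | 68% | 87% |

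| r needed for 90% at 1% | z | t, 12 df |
|---|---|---|
| Two-sided, one window | 0.83 | 0.87 |
| Two-sided, three windows | 0.75 | 0.81 |
| One-sided, one window | 0.80 | 0.85 |
| One-sided, three windows | 0.71 | 0.77 |

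**5. Colposcopy (conditional).** Suppose the similar assumptions mean ICC 0.07 and 8% means 13% vs 5%. With 430 × 50% = 215 women per control clinic and 20% fewer (172) per intervention clinic, SE = √[0.1131 × (1 + 214 × 0.07)/(7 × 215) + 0.0475 × (1 + 171 × 0.07)/(7 × 172)] = 0.0414. Unpaired power at one-sided 5% is 57% (t, 12 df) to 61% (z); the plan says at least 80%.

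**The case against.** The strongest reply is that the plan describes a change-from-baseline calculation, so an unpaired figure tests something the authors did not claim. Repeated rates from the same clinics may well be highly correlated, and if they are, 90% is attainable. This stands as far as it goes: the documents do not show that the trial is underpowered, and whether a correlation near 0.8 is realistic cannot be judged from them.

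It does not rescue the stated figure. If the 90% already includes the gain from pairing, the deciding input is missing. If it does not, as the sentence calling the estimates conservative suggests, the printed inputs give 28–48%. The text does not settle which is meant, so one can say only that the 90% may rest on an unstated correlation.

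Three smaller points also stand. The limits on the SD and the correlation depend on sidedness, which the plan leaves open, so both are shown. The three-window results rest on an assumed way of averaging. The colposcopy figure needs two readings that the text does not confirm and ignores pairing, so it is secondary.

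The primary-analysis sentence could also be read as both intervention arms together against control (14 vs 7 clinics). On the unpaired inputs that gives SE = √(0.25/97.0 + 0.2244/194.0) = 0.0611, and power at 1% of 43–52% two-sided or 54–61% one-sided, still well below 90%.

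**Conclusion.** The concern holds. On the printed inputs, an unpaired comparison at 16 points and the 1% level has 28–48% power, not 90%, and the missing-data statement comes to 56–74%, not more than 90%. This assumes that 16% means points and that clinics are equal in size. Both favour the plan: the relative reading gives 5–11%, and the enrollment section allows clinics from 200 to over 1000 clients. The power of the planned change analysis cannot be determined, because neither the SD of clinic-level change nor a pre-post correlation is given. The 90% should not be relied on until one of them is. The colposcopy shortfall is conditional on the two readings stated.

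**What to change.** Restate the primary and colposcopy power paragraphs:

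1. Say whether 16% means percentage points.
2. Give one alpha and sidedness for each primary comparison and use them throughout, including the missing-data sentence. The plan's 1% can stay.
3. Say how the three post windows are combined. From Family PACT claims for the eligible clinics, estimate the SD of clinic-level change in the three-month testing rate over those windows, and the three-month baseline rate itself.
4. Use a small-sample t reference: 12 df, or 18 df if variance is pooled over three arms.
5. Report the resulting power at 16 points, or the difference detectable with 90% power. At two-sided 1% the 90% stands only if the SD is no more than about 6.65 points (12 df) or 7.0 points (18 df). If the unpaired calculation with ICC 0.07 is kept, state 28–39% two-sided power at 16 points and a 90%-detectable difference of about 26 (z) to 29 (t, 12 df) points.
6. Give the colposcopy ICC as a number and recompute that figure.

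The cost is rewording and one calculation on claims data the team already holds. The stated power may become less favourable. The correction itself needs no extra clinics and no change to randomization, endpoint or test.

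### The primary power is quoted at 1% and then at an unadjusted 5%, while the analysis section names no multiplicity method; one familywise 5% rule should be stated and the power restated at it

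*Combined protocol and SAP*

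**What the plan says.** Three statements bear on the error rate of the primary comparisons of APP and of APP+PCA with the comparison clinics.

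- **Sample Size Estimates and Power Calculations, main statement.** The planned size "will be sufficient to provide 90% power to detect a between-arm difference as small as 16% as significant". The calculation "is based on a 1% significance level to account for the fact that there will be two pairwise comparisons with the control arm". No other reason is given for 1%.
- **Same section, next sentence.** With 10% missing data, "we will still retain more than 90% power to detect differences of this magnitude or larger between arms as significant at the 5% level". No adjustment is mentioned.
- **Analytic Methods, Data Analyses.** "Tests will be adjusted for multiple comparisons". Neither a method nor a familywise level is given, and 1% does not appear there.

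The other sizing inputs are "3010 per arm, seven clinics per arm, and an average of 430 women per clinic", a baseline rate of about 50%, an intracluster correlation of 0.07, and the assumption that "there will be no observed change in rates for control clinics during the testing period". The primary test is a t-test on clinic-level changes with allowance for clustering. Its sidedness is not stated; a one-sided level is stated only for colposcopy.

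**The concern.** Two comparisons with a control need at most 2.5% each under Bonferroni to hold 5% overall, and slightly less correction when the control is shared. The stated reason therefore does not lead to 1%. The following sentence goes the other way: 5% for each of two contrasts exceeds 5% overall and conflicts with the adjustment promised in the analysis section. The two power sentences cannot both describe one primary test, and the analysis section does not say which applies.

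With seven clinics per group, the critical value matters for power. If 1% were carried into the analysis, most of a 5% error allowance would go unused. If 5% each were, a false positive on at least one intervention would be nearly twice as likely as the conventional level allows. Either way, the reader has no primary power figure tied to a defined test.

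**Working it through.** **Inputs from the sample-size section.** Rates 0.50 and 0.34 (16% read as absolute points, the reading more favourable to the plan), k = 7 clinics per arm, m = 430 women per clinic, ICC = 0.07. Assumed here: two-sided tests, equal clinic variances, and the ICC applied to the compared rates. A pairwise t-test on 14 clinics has 12 df; a variance pooled over 21 clinics has 18 df. The plan states no df.

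**1. Familywise error.** For two contrasts with equal group sizes and a shared control, the test statistics correlate at 0.5. Integrating the bivariate t with 18 df gives:

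| Level per contrast | Familywise error |
|---|---|
| 1% | 1.9% |
| 2.5% | 4.6% |
| 5% | 8.9% |

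The two-sided Dunnett critical value for 5% overall is 2.40, equivalent to about 2.75% per contrast.

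**2. The plan's own figure, 90% power at 1%.** Design effect = 1 + 429 × 0.07 = 31.03. Effective sample = 3010 / 31.03 = 97.0 per arm.

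SE = √[(0.50×0.50 + 0.34×0.66) × (0.07 + 0.93/430) / 7] = √[0.4744 × 0.07216 / 7] = 0.0699.

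Noncentrality = 0.16 / 0.0699 = 2.29. Noncentral t power:

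| Test | Critical value | Power at 16 points |
|---|---|---|
| 1%, 12 df | 3.05 | 28% |
| 1%, 18 df | 2.88 | 31% |
| 2.5%, 12 df | 2.56 | 42% |
| 2.5%, 18 df | 2.45 | 46% |
| Dunnett 5% familywise, 18 df | 2.40 | 47% |
| 5% unadjusted, 12 df | 2.18 | 56% |
| 5% unadjusted, 18 df | 2.10 | 58% |

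The stated 90% is not reproduced. A normal approximation at 1% two-sided gives 37 to 39%, and a one-sided 1% t-test stays below 40%.

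**3. The missing-data sentence.** With 10% missing, m = 387 and SE = √[0.4744 × (0.07 + 0.93/387) / 7] = 0.0700, so the noncentrality is 2.28. Power at 5% two-sided is 56% (12 df), or 62% by the normal approximation. One-sided it is about 69 to 73%, depending on the approximation. None exceeds 90%. At 1% with 12 df, the loss of women moves power only from 27.6% to 27.5%, so missing data do not explain the move to 5%.

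**4. What would give 90%.** At 1% two-sided, the ICC would have to be about 0.016 (12 df) or 0.023 (normal). Alternatively, the clinic rates would have to correlate strongly between the pre and post windows. Take the change variance per clinic as 2(1 − r) × 0.07 × 0.25 + 0.93 × [0.25 + p(1 − p)]/430, with p the post-window rate. Power with 12 df is then:

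| Pre-post correlation r | 1% two-sided | 5% two-sided |
|---|---|---|
| 0 | 11% | 31% |
| 0.5 | 25% | 52% |
| 0.8 | 62% | 86% |
| 0.85 | 75% | 93% |
| 0.9 | 89% | 98% |

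The plan states no such correlation.

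**The case against.** **The 1% is a planning level.** It appears only in the sizing, and sizing at a strict alpha does not commit the trial to testing at it. The analysis section as written would allow Bonferroni, Holm or Dunnett at 5% overall. This stands. A reader might infer that the primary tests will be run at 1% each, or that the trial will run at 8.9% familywise error. The documents support neither; they leave the test level open.

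**A conservative alpha is valid.** A 1.9% familywise error is proper control, so preferring 5% is a matter of efficiency. That also stands for the 1% sentence taken alone. It does not reconcile that sentence with the next one.

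**The 5% might mean 5% overall.** The sentence does not say so, and its power is not reproduced even at an unadjusted 5% per contrast.

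**The sizing is described as conservative because the analysis will use within-clinic change.** Pairing helps only if the pre-post correlation is high enough. On the formula above, a correlation of 0.5 gives 25%, slightly below the unpaired 28%. The benefit depends on a figure that the plan does not give.

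**Dunnett is a preference.** At equal df it adds only 1 to 2 points over 2.5% each (47% against 46%). A reader who takes the stated 90% at face value might infer that Dunnett raises power to about 98%, or brings the detectable difference down to 13.3 points. Those figures add an assumed move from 12 to 18 df to the change in alpha, and they start from a 90% that the printed inputs do not support.

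**There may be more than two tests.** Three post-intervention windows are listed with none named as primary. Two contrasts over three windows would be six tests, or 5%/6 = 0.83% each. The plan does not justify 1% in this way, but the point is sound: a two-contrast rule holds 5% only for one window or summary.

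**Conclusion.** The point holds as an inconsistency in the stated error control and in the power tied to it. The 1% level is stricter than its only stated reason requires, the 5% sentence does not describe an adjusted test, and the analysis section settles neither the method nor the level.

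On the printed inputs, moving from 1% to 2.5% raises power for 16 points from about 28% to 42% (12 df). Pooling the variance and using Dunnett brings it to about 47%. The change is worth making, but it does not restore 90%; a reader should not infer that a better multiplicity rule rescues the design.

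These figures rest on a two-sided test, equal clinic variances, and the ICC of 0.07 applied to an unpaired comparison. A high pre-post correlation or a smaller ICC would raise them; a correlation below about 0.5 would lower them. The familywise error rates do not depend on the ICC or the effect size.

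**What to change.** In the sample-size section and in Data Analyses, before outcome data are examined:

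1. State one two-sided familywise 5% rule for APP and APP+PCA against the comparison clinics. Use either Holm with pairwise variances (smaller p-value against 2.5%, then the larger against 5%), or Dunnett on all 21 clinics if a common between-clinic variance is accepted.
2. Apply it to one named primary post-intervention window, or one summary of the three windows, and state that interim data will not be used for efficacy testing.
3. Restate every primary power figure at that level, including the 10%-missing sentence. Give the df and the assumed pre-post correlation, with a range if it is uncertain.

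The cost is a few sentences and a recalculation; no clinics are added. There are two downsides. Dunnett pools variance across randomised clinics and non-randomised, uncontacted comparison clinics, which may not share it; Holm with pairwise variances avoids pooling across all three groups. The restated power may also be less favourable than the figures now in the plan.

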### **Sample Size Estimates and Power Calculations**

The database for FY 2010/11 shows that 386 clinics fit the criteria with 89 sites available for arms 1-2 and 297 available for the comparison group. The mean number of female clients aged 21-29 years seen at the eligible clinics was 560 and the mean number of cytology specimens, colposcopic examinations and LEEP/cryoprocures for this age group was 297, 40, and 4, respectively. In 2012, the mean cytology interval was 19 months. Very few clinics had an interval >30 months. There were no differences for any of the above variables between those

sites eligible for intervention and those for comparison. These numbers have not changed significantly in the past 2 years and will be updated for the baseline assessment.

After enrolling 7 sites into each arm, we estimate that we would have approximately 2800-3500 women aged 21-29 years in each arm. For each arm, baseline cytology rate in this age group would be approximately 50%, rate of colposcopy procedures for those who had cytology would be 13%, and rate of LEEP/cryotherapy procedures for those referred to colposcopy would be 10%.

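### The stated 80% power for colposcopy does not reproduce from the plan's own inputs (about 57–61%), and it uses an unadjusted one-sided 5% level although the analysis section promises multiplicity adjustment

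*Combined protocol and SAP*

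**What the plan says.** The colposcopy calculation is the second power calculation in Sample Size Estimates and Power Calculations. It compares changes from baseline in three-month rates between arms and concludes that "we will retain at least 80% power to detect an intervention-related reduction in colposcopy rate as small as 8" per cent, "at the 5% (one-sided) significance level".

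Its assumptions are:
- For the control arm, "approximately 50% of women will receive cytology at baseline and follow-up in the control group" and "colposcopy rates will also remain unchanged at 13" per cent. The section's baseline figures give the denominator: "rate of colposcopy procedures for those who had cytology would be 13" per cent.
- For the intervention arm, "approximately 20% fewer women eligible for colposcopy at follow-up".
- ICC and loss to follow-up are described only as similar to those of the primary calculation, which uses an ICC of 0.07 and up to 10% missing data.

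The primary calculation differs in its level: it "is based on a 1% significance level to account for the fact that there will be two pairwise comparisons with the control arm".

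Data Analyses says that tests will be adjusted for multiple comparisons. Of the secondary endpoints, colposcopy included, it says: "These will be analyzed using a similar approach as adopted for the primary endpoint". It gives no sidedness and no alpha. Outcome (d) in that section defines the colposcopy rate as women aged 21–24 who receive colposcopy over all women aged 21–24.

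**The concern.** There are two separate questions. The first is whether the stated inputs give 80%. With seven clinics per arm and an ICC of 0.07, precision is governed by the number of clinics rather than the number of women, and an 8-point difference looks small for that. The second is whether the power refers to the planned test. The primary calculation lowers its level because there are two comparisons with control. The colposcopy calculation concerns the same comparisons and uses one-sided 5% with no adjustment.

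The interpretation of a null result is at stake. Reducing colposcopy is one of the Study Objectives. A reader who trusts the stated power would put the chance of missing a true 8-point fall at no more than 20%. On the plan's inputs it is about 40%, and higher once any adjustment is applied.

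**Working it through.** **Inputs from the plan**
- 7 clinics per arm, 430 women per clinic.
- Control: 50% have cytology, so 0.50 × 430 = 215 women per clinic; colposcopy rate 13%.
- Intervention: 20% fewer, so 0.80 × 215 = 172 women per clinic.
- Level: one-sided 5%.

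**Assumptions needed to run it**
- ICC 0.07, carried over from the primary calculation because the text says only that it is similar.
- The 8% reduction read as 8 points, 13% to 5%.
- Follow-up rates compared between arms, with no credit for pairing. The section describes pairing and baseline adjustment as gains beyond its stated figures.

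**Attempt to reproduce the 80%**

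Variance of an arm's mean rate = p(1 − p) × [ICC + (1 − ICC)/m] / 7.

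- Control: 0.1131 × (0.07 + 0.93/215) / 7 = 0.001201
- Intervention: 0.0475 × (0.07 + 0.93/172) / 7 = 0.000512
- SE = √(0.001201 + 0.000512) = 0.0414
- Standardised difference = 0.08 / 0.0414 = 1.93

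Power at one-sided 5%: normal, Φ(1.93 − 1.645) = **61%**; noncentral t with 12 df, **57%**. With 10% loss per clinic the figures are 61% and 57% again. The stated 80% is not reproduced.

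The difference detectable with 80% power at one-sided 5%, from 13%, is 9.8 points (normal) to 10.2 points (t).

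**Does another reading rescue it?** (one-sided 5%, t to normal unless noted)

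| Reading | Power |
|---|---|
| All 430 women per clinic as denominator, 13% to 5% | 58–63% |
| Unlimited women per clinic, ICC 0.07 | 59–64% |
| Both intervention arms pooled against control (range includes a pooled-variance z-test) | 64–74% |
| 8% as the resulting rate (13% to 8%) | 28–30% |
| 8% as a relative reduction (13% to 11.96%) | about 8% |
| All-women rates: 0.50 × 13% = 6.5% to 0.40 × 5% = 2.0% | 43–47% |

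None reaches 80%. The unlimited-women row shows that the clinic count is the limit.

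**What would give 80%?**
- A lower ICC: 0.040 (normal) or 0.035 (t), roughly half of 0.07.
- A change-score analysis with a high clinic-level pre/post correlation r. With a simple factor 2(1 − r) on the variance above, r must be 0.70 (normal) to 0.73 (t). With all four variances entered separately (13% at baseline in both arms, 13% and 5% at follow-up), r must be 0.78 to 0.81.

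For the four-variance version, one-sided 5%, t to normal:

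| r | Power |
|---|---|
| 0 | 32–35% |
| 0.5 | 50–54% |
| 0.7 | 66–71% |
| 0.8 | 79–83% |

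The simple factor gives 36–39% at r = 0. The documents state no r.

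**Effect of the level** (13% to 5%, SE 0.0414, t to normal)

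| Level | Power |
|---|---|
| One-sided 5% (stated) | 57–61% |
| Two-sided 5%, or one-sided 2.5% | 43–49% |
| Two-sided 2.5% (Bonferroni for two comparisons) | 31–38% |

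**The case against.** The strongest reply is that the plan describes a comparison of changes from baseline, whereas the 57–61% comes from follow-up rates alone. With a clinic-level correlation near 0.8 the change-score analysis would have about 80% power. That is arithmetically right, and it makes 57–61% one point in a range rather than the power of the design. It does not support the printed figure: no correlation is given, the section treats pairing and adjustment as extra power, and at low correlation the change-score analysis has less power.

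A second reply is that a similar ICC need not be 0.07. That also stands, but about half that value is needed, and the section calls its assumptions conservative. If a smaller ICC was used, it has not been disclosed.

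Third, the one-sided test is openly declared and the aim is directional. That is fair; one-sidedness is not in itself an error. What remains is the missing adjustment, set against the promise in Data Analyses. That promise comes before the secondary endpoints are introduced and reaches them through the similar-approach sentence. This is a reasonable reading, but an inference.

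Two stronger conclusions are tempting but not supported:
- A reader might infer that colposcopy will be tested at two-sided 1%, where power would be 18–26%. The 1% is a setting in the primary power calculation, with no sidedness given, and Data Analyses fixes no alpha for colposcopy.
- A reader might infer that the 20% fall in eligible women contradicts the primary effect (16 of 50 points, or 32%). The 16 points is a detectable difference, not an assumed effect, and using 32% changes power by less than one point.

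**Conclusion.** The point holds in a limited form: the stated power is not reproducible from the stated inputs. The gap is about 20 points on the most favourable reading of the effect, given an ICC of 0.07 and no credit for pre/post correlation. It is not shown that the design cannot have 80% power, because an undisclosed ICC or correlation could supply it.

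The mismatch in level needs no assumption about variance: the power is quoted without adjustment for the two comparisons, and the analysis section promises adjustment. The size of that effect depends on the alpha and sidedness finally chosen, which the documents leave open. The endpoint mismatch compounds it: the 13% refers to women with cytology in the 21–29 age group, while outcome (d) uses all women aged 21–24, so the calculation concerns a different rate in a different population.

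**What to change.** In Sample Size Estimates and Power Calculations, replace the 80% with either the recomputed power or the difference detectable with 80% power. State with it:
- the sidedness and the multiplicity-adjusted alpha for colposcopy, in the same terms in Data Analyses;
- the ICC for colposcopy, and the variance of the change or the pre/post correlation, with a range if no estimate exists;
- whether the 8% is absolute or relative;
- the denominator and age group, aligned with outcome (d).

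The Family PACT claims data used for the baseline assessment may allow the ICC and the correlation between quarters to be estimated. The cost is a less favourable stated figure; design and conduct need not change.
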